9.2 Handling of Missing Data

Observed Cases (OC) approach will be the only approach to handle missing data for both categorical and continuous efficacy endpoints in the study. The OC analysis will not impute values for missing evaluations, and thus a subject who does not have an evaluation on a scheduled visit will be excluded from the OC analysis for that visit. OC will not include values after a subject prematurely discontinues from study treatment.

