## 7.4 Statistical Analyses for Efficacy

---

The efficacy analysis will be conducted in the ITT Population and all statistical tests will be performed at a 2-sided significance level of 0.1. The 95% confidence interval of the treatment effect will be provided.

For categorical endpoints, comparisons will be made between each dose of cedirogant and placebo using Fisher's exact test. Non-responder imputation (NRI) incorporating multiple imputation (MI) to handle missing data due to COVID-19 (NRI-MI) will be the primary approach to handle missing values for categorical endpoints.

For continuous variables, comparisons of change and/or percent change from Baseline will be made between each dose of cedirogant and placebo based on the Mixed Model Repeated Measures (MMRM) adjusting for treatment, visit, and treatment-by-visit interaction as fixed factors, and Baseline value as a covariate. The MMRM will be the primary approach to handle missing values for continuous endpoints.

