2.2 Study Design Overview

[figure not shown]
This is a Phase 2, multicenter, randomized, double-blind, parallel-group, placebo-controlled dose ranging study that will evaluate the safety and efficacy of cedirogant in approximately 200 adult subjects with moderate to severe plaque psoriasis and who are candidates for systemic therapy or phototherapy.

The study is comprised of a 28-day Screening Period, a 16-week double-blind Treatment Period, and a 30-day Follow-up Period.

The schematic of the study is shown in [Figure 1](#).

This study was terminated early by AbbVie due to preclinical findings in the cedirogant 39-week dog toxicity study. The interim analysis pre-defined in the protocol will not be conducted. The final database lock will occur after the last on-going subject completes the follow-up phone call or withdraws from the study.

Figure 1. Study Schematic

PASI = Psoriasis Area Severity Index; PBO = placebo; QD = once daily

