2.3 Treatment Assignment and Blinding

All subjects will be assigned a unique identification number by the IRT at the screening visit. For subjects who rescreen, the screening number assigned by the IRT at the initial screening visit should be used. The IRT will assign a randomization number that will encode the subject's treatment group assignment according to the randomization schedule.

Subjects who meet eligibility criteria at Baseline will be randomized in a 1:1:1:1 ratio to 1 of the 4 treatment groups:

- Cedirogant 375 mg once daily (QD) (N = 50)
- Cedirogant 150 mg QD (N = 50)
- Cedirogant 75 mg QD (N = 50)

- Placebo QD (N = 50)

All active and placebo treatment will be taken orally (cedirogant 75 mg tablets and matching placebo). There is no stratification factor for the randomization.

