2.4 Sample Size Determination

Given the planned total sample size of 200 subjects (50 subjects in each arm), the study has more than 95% power to detect the treatment differences of 60% in PASI 75 in at least one cedirogant group versus placebo (PASI 75 response rate of 11%) using a two-sided significance level of 0.1 based on the 2-sample Chi-Squared test.

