9.3.3 Sensitivity and Supplementary Analyses of the Primary Efficacy Endpoint

No sensitivity and supplementary analyses of the primary efficacy endpoint will be conducted.

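### The SAP's Week 16 responder rate covers only on-drug, evaluated subjects but is labelled ITT; it omits earlier leavers along with sponsor cut-offs, and SAP 9.2 contradicts SAP 8.0

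*SAP*

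**What the plan says.** - SAP 9.2: the "Observed Cases (OC) approach will be the only approach to handle missing data for both categorical and continuous efficacy endpoints in the study". A subject without an evaluation at a visit drops out of that visit's summary, and values obtained after study treatment was stopped early are not used. The reason for stopping plays no part.
- SAP 8.0, for the primary and secondary endpoints: everything collected is used, whether or not study drug was stopped early.
- Protocol 7.4, for categorical endpoints: "Non-responder imputation (NRI) incorporating multiple imputation (MI) to handle missing data due to COVID-19 (NRI-MI) will be the primary approach" to missing values. A value missing for any reason other than COVID-19 therefore counted as non-response. For the primary endpoint the protocol also planned a sensitivity analysis with multiple imputation of all missing values.
- SAP 9.3.3: "No sensitivity and supplementary analyses of the primary efficacy endpoint will be conducted". SAP 9.4.3 likewise plans no sensitivity analysis for the secondary endpoints.
- SAP 2.2: "This study was terminated early by AbbVie due to preclinical findings in the cedirogant 39-week dog toxicity study". The version history in SAP 14.0 gives the early termination as the reason for moving from NRI-MI to observed cases.
- SAP 9.1 and 9.3.2 place the result in the ITT Population, which SAP 4.0 defines as all randomized subjects. SAP 9.1 reports the number of subjects, the percentage and a 95% confidence interval by visit, with no testing.

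**The concern.** The early stop leaves two kinds of subject without a usable Week 16 value. The first had a Week 16 date after the stop. Their loss has nothing to do with response, and counting them as failures would be wrong. The second had time to reach Week 16 but left earlier, for example for an adverse event or lack of efficacy. Under the protocol their missing values were non-responses. SAP 9.2 treats both kinds alike, and the reason given for the change covers only the first.

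At stake is how the doses are read against each other. The protocol's aim (section 2.1) is to explore efficacious and tolerated doses, and these descriptive rates are the only efficacy results. If leaving before Week 16 differs by dose, observed-case rates can differ between doses for that reason alone, and no planned efficacy table would show it.

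**Working it through.** **Inputs.** SAP 2.4: placebo PASI 75 of 11% and a difference of 60 points, hence 71% on active; "Given the planned total sample size of 200 subjects (50 subjects in each arm"); "using a two-sided significance level of 0.1 based on the 2-sample Chi-Squared test". SAP 2.3: subjects "randomized in a 1:1:1:1 ratio to 1 of the 4 treatment groups". The documents do not give the share d of subjects with time to reach Week 16 who leave before it, or the share c cut off by the stop. Both are assumed below.

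**The plan's own figure.** SAP 2.4 says "the study has more than 95% power to detect the treatment differences of 60% in PASI 75". The mean rate is (0.11 + 0.71)/2 = 0.41.
- Standard error under no difference: √(2 × 0.41 × 0.59/50) = 0.0984.
- Standard error under the alternative: √((0.11 × 0.89 + 0.71 × 0.29)/50) = 0.0779.
- (0.60 - 1.645 × 0.0984)/0.0779 ≈ 5.6, so power exceeds 99.99%.

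The stated lower bound is reproduced. The planning rates serve below only as illustrative response rates.

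**Effect of the denominator.** Let r be the rate when leavers count as failures. Responders are unchanged and the denominator shrinks by the factor 1-d, so observed cases give r/(1-d).

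| d, both arms | Active (r = 71%) | Placebo (r = 11%) | Difference (points) |
|---|---|---|---|
| 0% | 71.0% | 11.0% | 60.0 |
| 5% | 74.7% | 11.6% | 63.2 |
| 10% | 78.9% | 12.2% | 66.7 |
| 15% | 83.5% | 12.9% | 70.6 |
| 20% | 88.8% | 13.8% | 75.0 |

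**Unequal leaving.**
- 5% on active and 30% on placebo: 71/0.95 - 11/0.70 = 74.7 - 15.7 = 59.0 points, so the gap narrows.
- 20% on active and 5% on placebo: 71/0.80 - 11/0.95 = 88.8 - 11.6 = 77.2 points, so it widens.
- Two doses, each with r = 50%, and leaving of 20% and 5%: 50/0.80 = 62.5% and 50/0.95 = 52.6%, an apparent difference of 9.9 points.

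**Sponsor cut-offs.** If they are unrelated to response, omitting them leaves the rate unchanged. Counting them as failures gives r(1-c): 71% falls to 56.8%, 42.6% and 28.4% at c = 20%, 40% and 60%.

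**Worked counts (invented).** Of 50 randomized, 20 are cut off, 5 with time to reach Week 16 leave earlier, and 25 are evaluated on drug, of whom 18 respond. Observed cases give 18/25 = 72%; counting the 5 leavers as failures gives 18/30 = 60%; counting everyone missing as a failure gives 18/50 = 36%.

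**Off-drug values: SAP 8.0 against SAP 9.2.** Protocol 5.6 keeps subjects who stop drug in scheduled visits, so Week 16 values after stopping can exist. Let 71% of on-drug subjects respond, let d = 20% now be subjects who stopped drug but were evaluated, and let s be their response rate. Under SAP 9.2 the rate is 71%. Under SAP 8.0 it is 0.80 × 71 + 0.20 × s:
- s = 0: 56.8%, so SAP 9.2 is 14.2 points higher.
- s = 40%: 64.8%, so SAP 9.2 is 6.2 points higher.
- s = 71%: 71.0%, no difference.
- s = 90%: 74.8%, so SAP 9.2 is 3.8 points lower.

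**The case against.** The best defence is that this is a descriptive report of a stopped trial. SAP 2.1 defines no hypotheses or estimands for these endpoints, and SAP 9.1 and 13.0 rule out testing, so no error rate is affected. The number evaluated appears beside each percentage (SAP 9.1), and discontinuations are tabulated by primary reason and arm (SAP 5.0), so a careful reader can see that the denominator has shrunk. All of this stands, and it argues against replacing the observed-case table. But the SAP 5.0 counts are not limited to subjects with time to reach Week 16, so the missing comparison cannot be rebuilt from them.

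It can also be said that r/(1-d) is an upper bound. As a comparison with the protocol's non-responder rule it is exact. As a measure of bias against what leavers would have shown, it is the extreme case: at r = 71% and d = 20%, 20 of the 29 non-responders per 100 subjects must be leavers, and no leaver may have been a responder. That point stands too.

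A reader might infer that the reported rates are inflated as a matter of fact. The documents do not show this: they give no count of leavers, and omitting cut-offs unrelated to response inflates nothing. Nor are treatment failures discarded wholesale, since a non-responder still on drug and evaluated at Week 16 stays in the denominator.

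**Conclusion.** The point holds conditionally. Under SAP 9.2 the Week 16 rate describes subjects still on drug and evaluated, not all randomized subjects, and the stated reason for the change covers only those cut off by the stop. If 10% of subjects with time to reach Week 16 left earlier and count as failures, the planning rates of 71% and 11% would read 78.9% and 12.2%; at 20% they would read 88.8% and 13.8%. These sizes rest on assumed leaving rates, and at d = 0 the effect is nil. The gap between arms, or between doses, can grow or shrink, so a claim that observed cases favour cedirogant would go beyond the documents.

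The contradiction between SAP 8.0 and 9.2 needs no assumption. Both sections govern the same endpoints and give opposite rules for values after stopping drug.

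This does not call for a return to full non-responder imputation, which would count sponsor cut-offs as failures and err the other way. It calls for a cheap improvement to a descriptive report.

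**What to change.** 1. Reconcile SAP 8.0 and 9.2 on Week 16 values recorded after study drug was stopped, and apply the reconciled rule in every responder table.
2. Keep the observed-case table and add one supplementary table for PASI 75 and for each secondary responder endpoint. Its denominator is all randomised subjects whose scheduled Week 16 date, with visit window, fell before the sponsor's termination date. Membership then depends on randomisation date, not on outcome. Within it, a value missing for a reason other than termination or COVID-19 counts as non-response; a value missing because of termination or COVID-19 is left out and the number shown.
3. Report the number excluded from each Week 16 table by arm and reason, and label the observed-case rate as on-treatment observed cases rather than ITT.

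The cost is SAP wording and a little more programming. Primary discontinuation reasons are already summarised (SAP 5.0), and scheduled dates follow from randomisation. The termination date and visit window, which the documents reviewed do not give, must be written into the SAP. If sponsor termination is not a coded reason, it must be derived from dates. The downside is that rates in the supplementary table may be lower.

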9.3 Primary Efficacy Endpoint and Analyses

9.3.1 Primary Efficacy Endpoint

The primary endpoint is the achievement of $\geq 75\%$ reduction from baseline in PASI score (PASI 75) at Week 16.

9.3.2 Main Analysis of Primary Efficacy Endpoints

Descriptive summary statistics of the primary efficacy endpoint will be provided based on the ITT Population as described in Section 9.1.

9.3.3 Sensitivity and Supplementary Analyses of the Primary Efficacy Endpoint

No sensitivity and supplementary analyses of the primary efficacy endpoint will be conducted.

9.4 Secondary Efficacy Endpoints and Analyses

9.4.1 Secondary Efficacy Endpoints

The secondary endpoints are as defined in Section 3.2.

9.4.2 Main Analyses of Secondary Efficacy Endpoints

Descriptive summary statistics of the secondary efficacy endpoints will be provided based on the ITT Population as described in Section 9.1.

9.4.3 Sensitivity and Supplementary Analyses for Secondary Efficacy Endpoints

There will be no sensitivity analysis for the secondary efficacy endpoints.

9.5 Additional Efficacy Analyses

Descriptive summary statistics of the additional efficacy endpoints will be provided based on the ITT Population as described in Section 9.1.

9.6 Efficacy Subgroup Analyses

Descriptive summary statistics of each subgroup defined below will be provided for PASI 75 at Week 16, among the ITT Population:

- Age group (< 40 years, \geq 40)
- Sex (male, female)
- BMI (< 25, \geq 25)
- Baseline PASI (< median, \geq median)
- Baseline sPGA (3, 4)
- Baseline PSS (0, $>$ 0)
- Baseline NRS (< 4, \geq 4)
- Psoriatic arthritis (yes, no)
- Prior biologic (yes, no)

10.0 Safety Analyses

10.1 General Considerations

Safety data will be summarized for the Safety Population. Safety summaries will be presented by treatment group, including a total group for all subjects on active study drug. For the safety analysis, subjects are assigned to a treatment group based on the treatment actually received, regardless of the treatment randomized.

The overview of TEAEs, and potentially clinically important (PCI) findings in laboratory variables and vital sign variables will also be summarized among the Safety Populations.

Missing safety data will not be imputed.

10.2 Adverse Events

Adverse events (AEs) will be summarized and presented using primary MedDRA System Organ Classes (SOCs) and preferred terms (PTs) according to the version of the MedDRA coding dictionary used for the study at the time of database lock. The actual version of the MedDRA coding dictionary used will be noted in the AE tables and in the clinical study report. Specific adverse events will be counted once for each subject for calculating percentages, unless stated otherwise. In addition, if the same adverse event occurs multiple times within a subject, the highest severity and level of relationship to investigational product will be reported.

10.2.1 Treatment-Emergent Adverse Events

Treatment-emergent AEs are defined as any AE with the onset that is after the first dose of study drug and within 30 days after the last dose of study drug.

10.2.2 Adverse Event Overview

An overview of AEs will be presented consisting of the number and percentage of subjects experiencing at least one event for each of the following AE categories in the Safety Population:

- Any treatment-emergent AE
- Any treatment-emergent AE related to study drug according to the investigator
- Any severe treatment-emergent AE
- Any serious treatment-emergent AE
- Any treatment-emergent AE leading to discontinuation of study drug
- Any treatment-emergent AE leading to death
- Any treatment-emergent Safety topic of interest (STI)

- All deaths
- Deaths occurring \leq 30 days after last dose of study drug
- Deaths occurring $>$ 30 days after last dose of study drug.

10.2.3 Treatment-Emergent Adverse Events by SOC and/or PT

The number and percentage of subjects experiencing TEAEs will be tabulated using the MedDRA system organ class and preferred term, by maximum severity by SOC and PT, and by relationship to the study drug as assessed by the investigator by SOC and PT. Specific adverse events will be counted once for each subject for calculating percentages, unless stated otherwise. In addition, if the same adverse event occurs multiple times within a subject, the highest severity and level of relationship to investigational product will be reported.

In addition, treatment-emergent adverse events will be summarized by PT and sorted by decreasing frequency for the total active group.

10.2.4 Treatment-Emergent Adverse Events per Patient-Years of Exposure

Exposure-adjusted AEs per 100 patient-years will be provided, where AEs per 100 patient-years of exposure are defined as the number of AEs divided by the total exposure in 100 patient-years.

Note that one event per preferred term per day per subject will be counted in the calculation of the number of TEAEs (i.e., a preferred term will not be counted twice on the same day for the same subject). The exposure-adjusted TEAE rate per 100 patient-years is calculated as:

$$100 \times \frac{\text{Number of TEAEs}}{\text{Total Patient Years}},$$

where total patient years is defined as the sum of individual patient year, which is defined as the minimum of (the last dose date + 30 days, the end of study date) minus the first dose date +1, normalized by 365.25 and rounded to one decimal place.

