## 7.6 Statistical Analyses for Safety

---

All safety analyses will be performed on the Safety Population, based on the actual treatment received. Treatment-emergent adverse events (TEAEs), laboratory assessments, and vital signs will be summarized. Details will be described in the SAP.

A TEAE for the Safety Population is defined as an AE newly occurred or worsened after the first dose of study drug and within 30 days after the last dose of study drug. The number and percentage of subjects experiencing TEAEs and exposure-adjusted number of events (events per 100 year) will be tabulated using the MedDRA system organ class and preferred term, by severity, and by relationship to the study drug as assessed by the investigator. Summaries (including percentages and events per 100 patient years) of SAEs, deaths, and AEs leading to discontinuation will also be provided.

Mean change in laboratory and vital signs variables will be summarized. For selected laboratory parameters, a listing of all subjects with any laboratory value that is Grade  $\geq 3$  of NCI CTCAE v4.03 will be provided. Additional details for the safety analysis will be provided in the SAP.

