6.0 Study Drug Duration and Compliance

For the Safety population, duration of treatment will be summarized for each treatment group and for all active investigational study drug dose groups combined. Duration of treatment is defined for each subject as last dose date minus first dose date +1. Duration of treatment will be summarized using the number of subjects treated, mean, standard deviation, median, minimum and maximum. In addition, the number and percentage of subjects in each treatment duration interval (≥ 1 dose, ≥ 4 weeks, ≥ 12 weeks, ≥ 16 weeks) will be summarized.

Treatment compliance in the treatment period will be summarized by treatment group based on the Safety population. Treatment compliance for each subject is defined as the number of tablets actually taken divided by the number of tablets that should have been taken. For subjects who prematurely discontinued the study drug, the planned tablets will only be counted prior to that scheduled visit of discontinuation. The compliance rate will be summarized by treatment group.

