10.2.6 Safety Topics of Interest

Safety topics of interest will be summarized according to the search criteria are provided in [Appendix B](#).

The final list will be based on the most updated final version of cedirogant Product Safety Statistical Analysis Plan.

Treatment-emergent Safety Topics of Interest will be summarized by SOC and PT and listing format. Additionally, STI rates per 100 patient years of exposure will be provided for each STI category ([Appendix B](#)) in the AE overview summary.

Listings of safety topics of interest will also be provided.

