14.0 Version History

Table 1. SAP Version History Summary

Version	Date	Summary
1.0	18 Jan 2022	Original version
2.0	15 Dec 2022	
1. Section 2.0 Study Objectives and Design, due to early termination of the study, the planned interim analysis will not be conducted. The Final database lock will occur after the last on-going subject completes the follow-up phone call.2. Section 7.1 Demographics and Baseline Characteristics, removed Baseline TSQM-9, as TSQM-9 is not collected at baseline.3. Section 9.0 Efficacy Analyses, due to early termination of the study, there will be no comparison or statistical testing for all efficacy endpoints, only summary statistics will be provided. OC will be the approach to handle missing data for categorical and continuous efficacy endpoints instead of NRI-MI and MMRM, respectively.4. Section 10.2 Adverse Events, total patient years is defined as the sum of individual patient year, which is defined as the minimum of (the last dose date + 30 days, the end of study date) minus the first dose date +1, normalized by 365.25 and rounded to one decimal place.5. Section 10.3 added eDISH Plot of AST and removed shift tables.6. Section 12.0 Interim Analyses, due to early termination of the study, the planned interim analysis will not be conducted.

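### As written, SAP 10.2.4 rounds each subject's patient-years to one decimal before summing, when full exposure is only 0.389 years; only the displayed total should be rounded

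*SAP*

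**What the plan says.** SAP 10.2.4 gives the rate as 100 times the number of treatment-emergent adverse events (TEAEs) divided by total patient-years. It describes the denominator in one sentence: "where total patient years is defined as the sum of individual patient year, which is defined as the minimum of" the last dose date plus 30 days and the end-of-study date, "minus the first dose date +1, normalized by 365.25 and rounded to one decimal place". SAP 14.0 lists this definition among the version 2.0 changes and again ends it with "normalized by 365.25 and rounded to one decimal place". Neither document says anywhere that rounding applies only to the displayed total.

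The rates that depend on patient-years are these:

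- Protocol 7.6 says the "exposure-adjusted number of events (events per 100 year) will be tabulated" for TEAEs, and promises events per 100 patient-years for serious adverse events, deaths and events leading to discontinuation.
- SAP 10.2.6 adds that "STI rates per 100 patient years of exposure will be provided for each STI category" for the safety topics of interest (STIs). It does not define its own denominator, so the total in 10.2.4 is presumably the one meant.

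The planned schedule in SAP 2.2 is "a 16-week double-blind Treatment Period, and a 30-day Follow-up Period". SAP 6.0 handles treatment duration differently: "Duration of treatment is defined for each subject as last dose date minus first dose date +1", in days and with no rounding.

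**The concern.** First and last dose dates exist only for a subject, not for a group. The clause that uses them must therefore define the individual patient-year, and the rounding sits inside that clause, ahead of the sum. One decimal of a year is a very coarse unit here, because the step of 36.5 days is about a quarter of the longest planned exposure.

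Two things follow. If the sentence is programmed as written, the denominator of a reported safety rate is wrong. If one programmer follows the grammar and another rounds only the total, the same data give two sets of rates, and both programmers can claim to have followed the SAP.

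The study stopped early, so many subjects may have partial exposure. Rates per patient-year are meant to handle exactly that, and partial exposures are where per-subject rounding errors are largest.

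**Working it through.** The documents state no patient-year figure, so there is none to reproduce. The check applies the definition directly.

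**Inputs.** Treatment of 16 weeks and follow-up of 30 days (SAP 2.2); end of study 30 days after the last dose (Protocol 11); divisor 365.25 and one-decimal rounding (SAP 10.2.4); 50 subjects per arm as planned (SAP 2.3). The documents give no distribution of exposure, so every pattern of early stopping below is an assumption.

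**Formula.** For a subject treated for *w* weeks and followed for 30 days, days = 7*w* + 30 and years = days / 365.25. The rounded value changes at 0.05, 0.15, 0.25 and 0.35 years, that is at 18.3, 54.8, 91.3 and 127.8 days.

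**One subject.**

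| Exposure | Days | Years | Rounded | Error in denominator |
|---|---|---|---|---|
| 2 weeks + 30 days | 44 | 0.1205 | 0.1 | −17.0% |
| 4 weeks + 30 days | 58 | 0.1588 | 0.2 | +25.9% |
| 6 weeks + 30 days | 72 | 0.1971 | 0.2 | +1.5% |
| 8 weeks + 30 days | 86 | 0.2355 | 0.2 | −15.1% |
| 12 weeks + 30 days | 114 | 0.3121 | 0.3 | −3.9% |
| 16 weeks + 30 days | 142 | 0.3888 | 0.4 | +2.9% |

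The extremes over 31 to 142 days are adjacent: 54 days becomes 0.1 (−32.4%) and 55 days becomes 0.2 (+32.8%). An exposure of 18 days or less becomes 0.0, so the subject's events would count with no exposure behind them. That needs an end-of-study date soon after the first dose, because a subject followed for 30 days after a single dose already has 31 days.

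**One arm.**

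- Fifty completers: 50 × 0.4 = 20.0 against 50 × 142 / 365.25 = 19.44. The denominator is 2.9% too high and the rate 2.8% too low.
- Exposures spread evenly over 31 to 142 days: mean 0.2375 rounded against 0.2368 exact, an error of +0.3%.

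**Two arms.** The reported B/A rate ratio is the true ratio multiplied by (rounded/exact in A) / (rounded/exact in B). Assume 80% completers in A and 50% in B, with all other subjects in an arm stopping in the same week.

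- Both arms stop at Week 4. A: (0.8 × 0.4 + 0.2 × 0.2) / [(0.8 × 142 + 0.2 × 58) / 365.25] = 0.36 / 0.3428 = 1.0502. B: 0.30 / 0.2738 = 1.0958. Factor 1.0502 / 1.0958 = 0.958.
- Both arms stop at Week 8. A: 0.36 / 0.3581 = 1.0053. B: 0.30 / 0.3121 = 0.9612. Factor 1.046.
- The same calculation gives 1.033 at Week 2, 1.003 at Week 6 and 1.019 at Week 12.
- A stops at Week 4 and B at Week 8: 1.0502 / 0.9612 = 1.093. With the weeks swapped: 1.0053 / 1.0958 = 0.917.

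**Staggered entry with one common stop date.** A simulation assumed 40 subjects per arm, 10% against 40% dropout, and uniform entry over 150, 200 or 300 days, with 4,000 runs for each. The mean factor is 1.005. The 95% ranges are 0.960–1.052, 0.968–1.044 and 0.976–1.036.

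**If only the total is rounded.** Fifty completers give 19.44, shown as 19.4 (−0.2%). The largest possible error is 0.05 / total, which is 0.4% at 12.5 patient-years and smaller above that.

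**The case against.** The strongest reply is that this is loose drafting and not a wrong calculation. The sentence sets out to define total patient-years, one decimal is a natural display precision for an arm total near 19, and the closing words about scaling and rounding may have been meant for that total. The version history repeats the sentence and cannot settle the intent. Treatment duration in SAP 6.0 is a different quantity. All of that stands as an account of what may have been intended. It does not change what the sentence says, and it leaves two workable readings with different results.

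The reply on size is stronger. The SAP reports group rates, so the errors of about 32% for a single subject never appear in a table. The factors 0.917 and 1.093 need all non-completers in an arm to stop in the same week, with a different week in the other arm, and nothing in the documents suggests that. A study-wide stop with staggered entry would spread exposures out. With equal dropout in the same simulation model, the mean distortion between arms is about 0.0%, with a 95% range of about 0.96–1.04. The completer error is the same in every arm and cancels in comparisons between arms of completers. These points stand and limit the weight of the concern.

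It is also true that the zero-exposure case is marginal, that no safety test is planned, and that the counts and percentages in SAP 10.2.2 and 10.2.3 are untouched.

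**Conclusion.** The concern holds, as a minor point. Programmed as written, the rule gives a wrong denominator for the TEAE rates, and for the STI rates if, as seems intended, they use the same total. The expected effect on an arm's rate is usually a few percent: 2.8% too low for an arm of completers, and close to zero when exposures are evenly spread. A ratio between arms could move by up to about 9% under the contrived same-week patterns, and by about 5% at most within the 95% ranges of the staggered-entry simulation. The direction is not fixed and no systematic bias by arm is shown. All arm-level figures beyond the completer case rest on assumed exposure patterns. On the total-only reading the error is negligible, so what needs settling is where the rounding applies.

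**What to change.** Replace the definition in SAP 10.2.4 with wording such as:

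> Each subject's exposure in days runs from the first dose to whichever comes first, 30 days after the last dose or the end of study, counting both end dates. Total patient-years is the sum of these unrounded days divided by 365.25. Rates are computed from the unrounded total; only the total shown in the tables is rounded, to one decimal place.

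Add to SAP 10.2.6 that the STI rates use the same unrounded total. The cost is one definition in the SAP, a cross-reference and one line of code. No new data are needed and the conduct of the study does not change.
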